- b. If a participant cannot attend a scheduled in-person visit (with the exception of the Screening Visit, Day 1, and Day 22), a home visit is acceptable if performed by appropriately delegated study clinic staff.
- A complete physical examination, including height and weight, will be performed at the Screening Visit. Symptom-directed physical examinations will be performed at other study visits, if clinically indicated (see Section 8.3.1 for additional details).
- d. Vital sign measurements include assessment of systolic and diastolic blood pressure, pulse rate, respiratory rate, and body temperature (preferred route is oral) (see Section 8.3.2 for additional details).
- Blood samples for humoral immunogenicity must be collected prior to administration of the study intervention on Day 1 and Day 22.
- All participants will be randomized to receive 2 IM injections, one in each arm, in the deltoid muscle (Day 1) and 1 IM injection in the deltoid muscle (Day 22).
- At Day 1 and Day 22, eDiary instruction will be provided while the participant is onsite. The participant will be required to make eDiary entries approximately 30 minutes after each vaccination while at the study site and again that same evening when at home. Study participants will continue to record in the eDiary each day at the same time for 6 days following each vaccination. Local solicited ARs will be recorded separately for each injection. eDiary review by the site should occur daily on Day 1-Day 7 and Day 22-28. Additional review of the eDiary will occur at Day 8 and Day 29 between the site and the participant during the safety telephone calls.
- h. Medically qualified study staff will contact all participants. The participant will be interviewed according to the script. Information will be collected about occurrence of unsolicited AEs through 21 days postvaccination for either RSV or influenza, and the occurrence of MAAEs, SAEs, AESIs, or AEs leading to study discontinuation and concomitant medications associated with those events, and receipt of any nonstudy vaccinations at all points of contact.

ModernaTX, Inc. mRNA-1345-P304 Protocol

mRNA-1345

All concomitant medications and procedures will be recorded for 21 days following each vaccination (Day 1 through Day 43); all nonstudy vaccinations and concomitant medications relevant to or for the treatment of an SAE, AESI, or MAAE will be recorded from Day 1 through Month 6 after the last study injection/EoS.

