8. STUDY ASSESSMENTS AND PROCEDURES

- Study procedures and their timing are summarized in the SoA (Table 1). Protocol waivers or exemptions are not allowed.
- Adherence to the study design requirements, including those specified in the SoA (Table 1), is essential and required for study conduct.
- All screening evaluations must be completed and reviewed to confirm that potential participants meet all eligibility criteria. The Investigator will maintain a screening log to record details of all participants screened and to confirm eligibility or record reasons for screening failure, as applicable.
- Procedures conducted as part of the participant's routine clinical management (eg, blood count) and obtained before signing of the ICF may be utilized for screening or baseline purposes provided the procedures met the protocol-specified criteria and were performed within the timeframe defined in the SoA (Table 1).
- In the event of a significant study-continuity issue (eg, caused by a pandemic), alternate strategies for participant visits, assessments, medication distribution, and monitoring may be implemented by the Sponsor or the Investigator, as per local health authority/ethics requirements.
- Study results that could unblind the study will not be reported to investigative sites or other blinded personnel until the study has been unblinded.
- If a visit cannot be scheduled within the indicated allowable window and/or the participant misses the visit, this is considered a protocol deviation. However, the visit should still be completed, if possible, to collect study data. Subsequent visits should be scheduled at the originally planned number of days after Day 1 defined in the SoA (Table 1).

The maximum amount of blood collected from each participant over the duration of the study, including any extra assessments that may be required, will not exceed blood limits specified by local regulations. Sample collection on Day 1 and Day 22 (ie, blood) must be performed prior to study intervention dosing.

Repeat or unscheduled samples may be taken for safety reasons or for technical issues with the samples. Further details are provided in both the ICF and Laboratory Reference Manual.

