6.2.7. Important Protocol Deviations

Important protocol deviations are a subset of protocol deviations that may significantly impact the completeness, accuracy, and/or reliability of the study data or that may significantly affect a participant's rights, safety, or well-being. Important protocol deviations will be identified based on the protocol at the start of the study and updated during the conduct of the study, and will be finalized before database lock (DBL).

The number and percentage of the participants with any important protocol deviations in each category will be provided by treatment group based on the Randomized Set.

A subset of important protocol deviations, which impact critical or key study data and thus lead to exclusion of participants from the PP set, may include (but are not limited to) the following:

- Received a wrong Day 1 study intervention or Day 22 study intervention
- Enrolled/dosed at two investigational sites
- Did not have a baseline immunogenicity assessment
- Did not have any postinjection immunogenicity assessment
- Received prohibited medication (s) affecting immune responses

The important protocol deviations leading to exclusion from the PP set will be determined and documented by Sponsor prior to DBL and unblinding. Reasons of exclusion from PP Set for immunogenicity will be summarized by treatment group.

Significant protocol deviations will be presented in a listing.

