9.7. Appendix G Estimands and Estimand Specifications

Table 4: Intercurrent Events

Label	Intercurrent Event Type
IcEv1 (Early discontinuation)	Discontinued early from study.
IcEv2 (Prohibited medications)	Received any concomitant medications and non-study vaccines deemed to affect immune responses.
IcEv3 (Important protocol deviation impacting key study data)	Received a wrong Day 1 study intervention or Day 22 study intervention, enrolled/dosed at two investigational sites, did not have a baseline immunogenicity assessment or did not have any post-injection immunogenicity assessments.
IcEv4 (Immunogenicity assessments falling out of visit window)	Had immunogenicity assessments falling out of analysis visit windows described in Appendix B.

Abbreviation: IcEv: intercurrent event.

Table 5: Summary of Primary Immune Estimands with Rationale for Strategies to Address Intercurrent Events

Objective: To evaluate the impact of coadministered HD quadrivalent seasonal influenza vaccine on the immune response to mRNA-1345 RSV vaccine against RSV-A and RSV-B			
Estimand Label	Primary Immune Estimand 1a (on the PP Set)	Supportive Immune Estimand 1b (on the FAS Set)	
Estimand Description	Immune response to mRNA-1345 RSV vaccine measured as GMR of RSV-A and RSV-B nAbs at Day 22 (Arm 1) or Day 43 (Arm 2) in adults ≥65 years old who receive the assigned study intervention dose at both Day 1 and Day 22, comply with immunogenicity blood sampling to have a baseline and at least 1 postinjection assessment, and have no important protocol deviations impacting the immune response.	Immune response to mRNA-1345 RSV vaccine measured as GMR of RSV-A and RSV-B nAbs at Day 22 (Arm 1) or Day 43 (Arm 2) in adults ≥65 years old who receive any study intervention dose irrespective of any important protocol deviations impacting the immune response.	
Target Population	Adults ≥65 years old who receive the assigned study intervention dose at both Day 1 and Day 22, comply with immunogenicity blood sampling to have a baseline and at least 1 postinjection assessment, and have no important protocol deviations impacting the immune response.	Adults ≥65 years old who receive any study intervention dose irrespective of any important protocol deviations impacting immune response.	
Endpoint	GMT of serum RSV-A and RSV-B nAbs at Day 22 (Arm 1) or Day 43 (Arm 2).	As per Estimand 1a.	

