Treatment Conditions	Fluzone HD + mRNA-1345/Placebo (Test) vs. Fluzone HD + Placebo/mRNA-1345 (Reference)	As per Estimand 1a.	

Population-Level Summary	Immune response to mRNA-1345 RSV vaccine defined as GMR of RSV-A and RSV-B nAbs using an ANCOVA model on the log-transformed tiers at Day 22 (Arm 1) or Day 43 (Arm 2), with the treatment group as a fixed variable, adjusted for stratified age group used for randomization and log-transformed baseline tiers.	As per Estimand 1a.
Intercurrent Event Strategy		
IcEv1 (Early discontinuation)	Treatment policy (Including all data collected)	Treatment policy (Including all data collected)
IcEv2 (Prohibited medications)	Principal stratum (Excluding participants)	Treatment policy (Including all data collected)
IcEv3 (Important protocol deviation impacting key study data)	Principal stratum (Excluding participants)	Treatment policy (Including all data collected)
IcEv4 (Immunogenicity assessments falling out of visit window)	Hypothetical (Excluding related data)	Treatment policy (Including all data collected)
Rationale for Strategies	This estimand seeks to understand immune response impact during the coadministered HD quadrivalent seasonal influenza vaccine in adults aged 65 or older who receive the assigned study intervention dose at both Day 1 and Day 22 and comply with key protocol criteria. A principal stratum is used to exclude participants with prohibited medications affecting immune responses or important protocol deviations impacting key study data so that analysis is a sub-population composed of participants free from such intercurrent events. For early discontinuation, all collected data are included. Immunogenicity assessments falling out of visit window are excluded.	A treatment policy strategy is used for following up immune response including all participants who receive any study intervention dose irrespective of whether they subsequently were found not to strictly meet the key protocol criteria. There is interest in understanding immune response in the light of poor compliance which may happen in clinical practice.
	impact of coadministered mRNA-1345 RSV vaccine on that vaccine-matched influenza A and B strains	ne immune response to HD quadrivalent seasonal
Estimand Label	Primary Immune Estimand 2a (on the PP Set)	Supportive Immune Estimand 2b (on the FAS Set)

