Estimand Description	Immune response to HD quadrivalent seasonal influenza vaccine measured as GMR of anti-HA Abs as measured by HAI assay at Day 22 in adults ≥65 years old who receive the assigned study intervention dose at both Day 1 and Day 22, comply with immunogenicity blood sampling to have a baseline and at least 1 postinjection assessment, and have no important protocol deviations impacting the immune response.	Immune response to HD quadrivalent seasonal influenza measured vaccine as GMR of anti-HA Abs as measured by HAI assay at Day 22 in adults ≥65 years old who receive study intervention dose irrespective of any important protocol deviations impacting the immune response.
Target Population	Adults ≥65 years old who receive the assigned study intervention dose at both Day 1 and Day 22, comply with immunogenicity blood sampling to have a baseline and at least 1 postinjection assessment, and have no important protocol deviations impacting the immune response.	Adults ≥65 years old who receive any study intervention dose irrespective of any important protocol deviations impacting immune response.
Endpoint	GMT of serum anti-HA Abs by HAI assay at Day 22.	As per Estimand 2a.
Treatment Conditions	Fluzone HD + mRNA-1345/Placebo (Test) vs. Fluzone HD + Placebo/mRNA-1345 (Reference)	As per Estimand 2a.
Population-Level Summary	Immune response to HD quadrivalent seasonal influenza vaccine defined as GMR anti-HA Abs by HAI assay using an ANCOVA model on the log-transformed tiers at Day 22, with the treatment group as the fixed variable, adjusted for stratified age group used for randomization and log-transformed baseline tiers.	As per Estimand 2a.
Intercurrent Event Strategy		
IcEv1 (Early discontinuation)	Treatment policy (Including all data collected)	Treatment policy (Including all data collected)
IcEv2 (Prohibited medications)	Principal stratum (Excluding participants)	Treatment policy (Including all data collected)
IcEv3 (Important protocol deviation impacting key study data))	Principal stratum (Excluding participants)	Treatment policy (Including all data collected)
IcEv4 (Immunogenicity assessments falling out of visit window)	Hypothetical (Excluding related data)	Treatment policy (Including all data collected)

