Rationale for Strategies	This estimand seeks to understand immune response impact during the coadministered HD quadrivalent seasonal influenza vaccine in adults aged 65 or older who receive the assigned intervention dose at both Day 1 and Day 22 and comply with key protocol criteria. A principal stratum is used to exclude participants with prohibited medications affecting immune responses or important protocol deviations impacting key study data so that analysis is a sub-population composed of participants free from such intercurrent events. For early discontinuation, all collected data are included. Immunogenicity assessments falling out of visit window are excluded.	A treatment policy strategy is used for following up immune response including all participants who receive any study intervention dose irrespective of whether they subsequently were found not to strictly meet the key protocol criteria. There is interest in understanding immune response in the light of poor compliance which may happen in clinical practice.
--------------------------	---	--

Table 6: Summary of Primary Safety Estimands with Rationale for Strategies to Address Intercurrent Events

Objective: To evalua vaccine (Fluzone® H	te the safety and tolerability of mRNA-1345 RSV vaccine cosID)	administered with a HD quadrivalent seasonal influenza
Estimand Label	Safety Estimand 3a	Safety Estimand 3b
Estimand Description	Proportion of participants reporting any solicited local ARs up to 7 days after each study injection (Day 1 or Day 22).	Proportion of participants reporting any unsolicited AEs up to 21 days after each study injection (Day 1 or Day 22).
	• Proportion of participants reporting any solicited systemic ARs up to 7 days after each study injection	 Proportion of participants reporting any MAAEs up to Day 202/EOS.
	(Day 1 or Day 22).	 Proportion of participants reporting any AESI up to Day 202/EOS.
		 Proportion of participants reporting any SAEs up to Day 202/EOS.
		 Proportion of participants reporting any AEs leading to discontinuation from the study up to Day 202/EOS.
Target Population	Adults ≥65 years old who receive any study intervention and contribute any solicited AR data.	Adults ≥65 years old who receive any study intervention.
Endpoint	• Incidence of solicited local ARs up to 7 days after each study injection.	Incidence of unsolicited AEs up to 21 days after each study injection.

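### Primary influenza Estimand 2a requires the assigned Day 22 injection, which follows the scheduled Day 22 HAI blood sample and cannot affect that titer

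*SAP*

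**What the plan says.** The four influenza coprimary endpoints are HAI titers at Day 22 in both arms (SAP 3.1.2 and 4.2). SAP 6.4.2 analyzes them on the Per-protocol (PP) Set to estimate Estimand 2a. SAP Appendix G, Table 5, describes 2a as a comparison by "HAI assay at Day 22 in adults ≥65 years old who receive the assigned study intervention dose at both Day 1 and Day 22". The target population repeats the two-dose condition, and the rationale refers again to adults "who receive the assigned intervention dose at both Day 1 and Day 22 and comply with key protocol criteria".

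The order of events on Day 22 is fixed. Protocol 1.3, in a footnote repeated in SAP Appendix F, states: "Blood samples for humoral immunogenicity must be collected prior to administration of the study intervention on Day 1 and Day 22". Protocol section 8 repeats it: "Sample collection on Day 1 and Day 22 (ie, blood) must be performed prior to study intervention dosing".

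Three rules bear on the Day 22 injection:

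- SAP 6.2.7 lists, among deviations leading to exclusion from the PP Set, "Received a wrong Day 1 study intervention or Day 22 study intervention". Table 4 of Appendix G makes the same event part of intercurrent event 3 (IcEv3): "Received a wrong Day 1 study intervention or Day 22 study intervention, enrolled/dosed at two investigational sites". Under 2a, participants with IcEv3 are excluded.
- SAP 5.3 requires that PP participants receive their assigned dose as the protocol lays down. There is one PP Set for RSV and influenza.
- For early discontinuation (IcEv1), the rationale for 2a says: "For early discontinuation, all collected data are included".

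**The concern.** A participant with correct Day 1 injections, a baseline and an in-window HAI sample has a complete influenza outcome before the Day 22 syringe is used. What happens next (placebo in Arm 1, mRNA-1345 in Arm 2) bears on Arm 2's RSV endpoint but not on that influenza titer. Estimand 2a nevertheless carries the same two-dose condition as RSV Estimand 1a. For influenza the condition protects nothing, and it selects participants on an event that follows the measurement.

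This matters because all six coprimary endpoints must succeed (SAP 6.5) and are judged on the PP Set. The influenza seroconversion rates (SCR), which come first in the secondary testing order, use the same set.

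The situation can arise. Protocol 5.4 allows dosing to be stopped at the visit, and Protocol 7.1 asks that such participants stay in follow-up where possible.

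**Working it through.** **1. Who is affected.** Take participants with valid Day 1 injections, a baseline and a scheduled, in-window Day 22 HAI sample:

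| After the Day 22 sample | Rule that applies | Result under 2a |
|---|---|---|
| Wrong injection given | SAP 6.2.7; IcEv3 | Excluded explicitly |
| Injection missed, stays in study | Target population of 2a; dosing condition in SAP 5.3 | Excluded by that wording only; not named in 6.2.7 or IcEv3 |
| Injection missed, leaves study | Target population against IcEv1 | Contradictory: excluded by one, included by the other |

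In none of the three can the later event alter the titer. There is one exception to the ordering. Appendix B maps an unscheduled sample to Day 22 if it falls on study days 15 to 36 counted from the Day 1 injection. Such a sample could be taken after the Day 22 injection, and then the injection does count.

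**2. The plan's own power.** Inputs from SAP 4.3: 950 per arm, 10% lost to the PP Set, SD 1.5 on the natural log scale, GMR 0.9, margin 1.5, 2-sided alpha 0.05.

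- n = 950 × 0.90 = 855 per arm.
- Distance to the limit: ln(0.9) − ln(1/1.5) = 0.300.
- Standard error: 1.5 × √(2/855) = 0.0725.
- Power ≈ Φ(0.300/0.0725 − 1.96) = 0.985; the noncentral t gives 0.9852. The stated 98.5% reproduces.
- Overall: 0.985^6 = 0.913, the stated 91.3%. The plan's figure thus matches six independent endpoints. With the unrounded 0.9852 the product is 0.914.

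**3. Power if the lost titers are kept.** The documents do not give the share of PP loss that arises only from the Day 22 injection. I assume 1% to 5% of each arm. The upper end would be half of the whole planned 10% loss. RSV stays at 855.

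| Recovered share (assumed) | Influenza n per arm | Power per strain | Overall power |
|---|---|---|---|
| 0 | 855 | 0.9852 | 0.9852^6 = 0.914 |
| 1% | 950 × 0.91 = 864 | 0.9860 | 0.9852² × 0.9860⁴ = 0.917 |
| 5% | 950 × 0.95 = 902 | 0.9889 | 0.9852² × 0.9889⁴ = 0.928 |

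The gain is 0.1 to 0.4 points per strain and 0.3 to 1.4 points overall. The six titers come from the same people, so independence overstates the overall gain. With an assumed pairwise correlation of 0.3 to 0.7, the gain at 5% is about 0.7 to 1.2 points.

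**4. Selection.** Let f1 and f2 be the shares of sampled participants dropped in Arms 1 and 2. Let D1 and D2 be their mean log titer minus that of the participants kept. Ignoring covariate adjustment, the mean over all sampled participants in an arm is the mean of those kept plus f × D, so

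ln(GMR among kept) − ln(GMR among all) = −(f1 × D1 − f2 × D2).

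This is zero only when the two products are equal. Equal loss alone is not enough if D differs between arms. The documents give no value for any of the four terms, so neither size nor sign can be derived.

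**The case against.** The strongest reply is that little is lost and the plan already has a remedy. The supportive analysis of the coprimary endpoints on the Full Analysis Set (Estimand 2b; SAP 6.4 and 6.4.2.2) is unconditional and keeps these titers. That stands as mitigation. But 2b is supportive only and also gives up every other PP safeguard, so it does not repair 2a. For the SCR endpoints, such an analysis is only optional and depends on the PP and FAS counts differing by more than 10%.

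Second, the route is narrow. Protocol 5.4 calls for the visit to be rescheduled when health temporarily precludes dosing, and Protocol 8.3.2 puts vital signs before blood collection where applicable. Some participants would be deferred before any sample. Where fever or infection stops dosing, the cause may precede the sample even though the missed dose follows it. This stands, and it is a reason to expect small numbers.

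Third, one PP Set across six endpoints that must all succeed is simpler. That is true, but the SAP already uses antigen- and arm-specific baselines and windows, and injection-specific safety subsets.

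Two stronger readings are tempting but not supported:

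- A reader might infer from Protocol 6.9.3 that nonstudy vaccines or immunoglobulins given after the HAI sample must also remove the participant. That section says only that such products may affect evaluability. The SAP limits exclusion to products judged to affect immune responses, with the decision documented before database lock and unblinding. The documents do not tie these products to the sample date, but they mandate no such exclusion.
- A reader might infer that the rule biases the influenza comparison in a known direction, because Day 1 treatment differs by arm and could produce unequal loss. The documents give neither the loss by arm nor the titers of those lost.

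**Conclusion.** The point holds. The decisive influenza estimand is conditioned on an injection that, for every scheduled sample, comes after the outcome. A wrong Day 22 injection excludes the participant outright. A missed one does so only through the target population and PP dosing wording, and for participants who leave undosed after the sample the SAP contradicts itself, so two programmers could code the primary analysis differently.

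The consequence is probably small. Under the assumed 1% to 5% recovery, power per strain goes from 98.5% to between 98.6% and 98.9%. Overall power gains at most about 1.4 points with independent endpoints, and less with correlated ones. Selection bias is possible but cannot be sized or signed from the documents. The case for change is that the condition has no validity purpose for influenza and is cheap to remove. It does not rest on a threat to the study's power.

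**What to change.** Define an influenza PP Set for the four GMT coprimary endpoints and the four SCR endpoints. It should require correct Day 1 injections, a Day 1 baseline and an in-window Day 22 HAI sample. Exclude only for deviations or prohibited products on or before the sample used. Let the Day 22 injection count only when the sample mapped under Appendix B was taken after it.

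In Estimand 2a, reduce the dosing condition to Day 1 in the description, target population and rationale. Keep the two-dose condition for RSV Estimand 1a in both arms: Arm 2's RSV outcome depends on the Day 22 dose, and filtering one arm alone would make the arms differ. State for both estimands how IcEv1 relates to the target population. Align SAP 5.3, 6.2.7 and Appendix G with Protocol 9.4, which defines a single PP Set.

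The cost is one extra population flag, two PP counts to report, and slightly different sets behind the RSV and influenza results. Protocol section 9 calls for an amendment when methods for primary or secondary hypotheses change before unblinding, so the protocol wording must be changed in that period too.
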